10.5.2 Experimental phase

Visit 1

- Re-check of the inclusion and exclusion criteria (see section 8.2 and 8.4);
- Physical examination (see section 10.4.3);
- Vital signs (see section 10.4.4);
- Documentation of demographic data;
- Update of previous and concomitant medication;
- Recording of AEs/SAEs;
- Identification of treatment areas;
- Marking of test areas;
- Shaving of test areas;
- TrichoScan imaging without hair dye;
- Safety assessment and local tolerance assessment (see section 10.4);

Visit 2

- Update of previous and concomitant medication;
- Recording of AEs/SAEs (record potential AEs also 15 min after first application);
- Safety assessment and local tolerance assessment (see section 10.4);
- Randomisation
- Identification of selected treatment areas;
- Marking of selected treatment areas;
- TrichoScan imaging including hair dye
- IP application

Visit 3 - 21

- Update of previous and concomitant medication;
- Recording of AEs/SAEs;
- Safety assessment and local tolerance assessment (see section 10.4);
- Optinal: repeat of tattooing, if necessary;
- Identification of selected treatment areas;
- IP application

Visit 22

- Update of previous and concomitant medication;
- Recording of AEs/SAEs;
- Safety assessment and local tolerance assessment (see section 10.4);
- Identification of selected treatment areas;
- IP application

Visit 23

- Update of previous and concomitant medication;
- Recording of AEs/SAEs;
- Safety assessment and local tolerance assessment (see section 10.4);
- Identification of selected treatment areas;
- Marking of selected treatment areas;
- Shaving ot test areas
- TrichoScan Image without hair dye

Visit 24

- Update of previous and concomitant medication;
- Recording of AEs/SAEs;
- Safety assessment and local tolerance assessment (see section 10.4);
- Identification of selected treatment areas;
- Marking of selected treatment areas;
- TrichoScan imaging including hair dye
- IP application

Visit 25 - 36

- Update of previous and concomitant medication;
- Recording of AEs/SAEs;
- Safety assessment and local tolerance assessment (see section 10.4);
- Optinal: repeat of tattooing, if necessary;
- Identification of selected treatment areas;
- IP application

Visit 37

- Update of previous and concomitant medication;
- Recording of AEs/SAEs;

- Safety assessment and local tolerance assessment (see section 10.4);
- Identification of selected treatment areas
- Shaving ot test areas;
- TrichoScan imaging without hair dye;

Visit 38

- Update of previous and concomitant medication;
- Physical examination (see section 10.4.3);
- Vital signs (see section 10.4.4);
- Recording of AEs/SAEs;
- Safety assessment and local tolerance assessment (see section 10.4);
- Blood and urine sampling for assessment of safety laboratory parameters;
- TrichoScan imaging including hair dye

EoT visit (if not identical with Visit 38 due to early discontinuation)

- Update of previous and concomitant medication;
- Physical examination (see section 10.4.3);
- Vital signs (see section 10.4.4);
- Recording of AEs/SAEs;
- Safety assessment and local tolerance assessment (see section 10.4);
- Blood and urine sampling for assessment of safety laboratory parameters;

Subjects should refer to the clinical site three times a week at an interval of at least 1 day.

10.6 Criteria for discontinuation of subject due to local intolerance and further proceedings

In case of adverse events, which bring the subject at risk or might confound the results of the trial the subject should be discontinued. The subject should be referred to his private practitioner for further diagnostics.

11 ADVERSE EVENTS

11.1 **Definitions**

11.1.1 Adverse Event

Any untoward medical occurrence in a subject or clinical trial subject administered a medicinal product and which does not necessarily have a causal relationship with this treatment.

Comment: An AE can therefore be any unfavourable and unintended sign (including an abnormal laboratory finding), symptom, or disease temporally associated with the use of an investigational medicinal product, whether or not considered related to the investigational medicinal product.

11.1.2 Adverse Reaction

All untoward and unintended responses to an investigational medicinal product related to any dose administered.

Comment: All AEs judged by either the reporting Investigator or the Sponsor as having a reasonable causal relationship to a medicinal product qualify as adverse reactions. The expression reasonable causal relationship means to convey in general that there is evidence or argument to suggest a causal relationship.

11.1.3 Unexpected Adverse Reaction

An adverse reaction, the nature or severity of which is not consistent with the applicable product information (e.g. IB for an unauthorised IP or summary of product characteristics for an authorised product).

Comment: When the outcome of the adverse reaction is not consistent with the applicable product information this adverse reaction should be considered as unexpected.

11.1.4 Serious Adverse Event

Any untoward medicinal occurrence or effect that at any dose:

- Results in death
- Is life-threatening
- Requires hospitalisation or prolongation of existing hospitalisation
- Results in persistent or significant disability or incapacity
- Is a congenital anomaly or birth defect
- May not be immediately life-threatening or result in death or hospitalization but may jeopardize the subject or may require intervention to prevent one of the other outcomes listed in the definition above.

Comments: Life-threatening in the definition of an SAE or serious adverse reaction refers to an event in which the subject was at risk of death at the time of event; it does not refer to an event which hypothetically might have caused death if it was more severe.

Medical judgement should be exercised in deciding whether an AE/reaction is serious in other situations. Important AEs/reactions that are not immediately life-threatening or do not result in death or hospitalisation but may jeopardise the subject or may require intervention to prevent one of the other outcomes listed in the definition above, should also be considered serious.

11.2 **Reporting of Adverse Events**

All trial subjects will be carefully monitored for the occurrence of AEs during the trial period, from intake of the first dose of IP until the last dose of IP for each subject. Previously reported AEs will be followed up and assessed as "recovered" or "not recovered". The Investigator will collect AEs with a non-leading question such as "have you experienced any new health problems or worsening of existing conditions" as well as reporting events directly observed or spontaneously volunteered by subjects.

Clearly related signs, symptoms and abnormal diagnostic procedure results should be grouped together and reported as a single diagnosis or syndrome whenever possible.

All AEs including but not limited to events reported by the subject, or reported in answer to an open question by the Investigator or member of this team, which fall into any of the above definitions must be recorded as an AE in the source data and the eCRF and should include the following information:

- Brief description of the event (diagnosis)
- Start date (and time, if relevant)
- Stop date (and time, if relevant) (or resolution)
- Severity
- Action taken regarding trial treatment
- Opinion on causality
- Seriousness
- Outcome

Severity

Severity describes the intensity of an event, and will be assessed as:

Mild

The AE does not interfere in a significant manner with the subject's normal functioning level. It may be an annoyance.

Moderate

The AE produces some impairment of function but not hazardous to health. It is uncomfortable and/or an embarrassment.

Severe

The AE produces significant impairment of functioning or incapacitation and/or it is a hazard to the subject.

If an AE changes in severity, the worst severity should be reported.

Causality

Causality will be assessed as:

Probable

A clinical event, including laboratory test abnormality, with a reasonable time sequence to administration of the drug, unlikely to be attributed to concurrent disease or other drugs or

chemicals, and which follows a clinically reasonable response on withdrawal (de-challenge). Re-challenge information is not required to fulfil this definition.

Possible

A clinical event, including laboratory test abnormality, with a reasonable time sequence to administration of the drug, but which could also be explained by concurrent disease or other drugs or chemicals. Information on drug withdrawal may be lacking or unclear.

Unlikely

A clinical event, including laboratory test abnormality, with a temporal relationship to drug administration which makes a causal relationship improbable, and in which other drugs, chemicals or underlying disease provide plausible explanations.

Follow-up of Subjects after Adverse Events

Ongoing AEs will not be followed after the date of trial termination for a subject, unless the Investigator assesses the AE as relevant to follow from a trial perspective. The date when the Investigator considers one of these outcomes to have occurred for the last ongoing AE for a subject will be considered the last visit for this subject, and the outcome should be recorded in the source data and the eCRF.

Abnormal Laboratory Values/Vital Signs

An asymptomatic abnormal laboratory/vital sign finding should only be reported as an AE if it is clinically significant, if it fulfils the criteria for an SAE or if it causes the subject to discontinue the trial.

Clinically significant abnormal findings at Visit 1 will be recorded in the source data and on the medical and surgical history page in the eCRF. New or worsening clinically significant abnormal findings at all Visits will be recorded in the source data and on the AE page in the eCRF.

If an abnormal laboratory/vital sign value is associated with clinical signs and symptoms, the sign/symptom should be reported as an AE and the associated laboratory/vital sign result should be considered additional information.

11.3 **Reporting of Serious Adverse Events**

The Investigator is responsible for ensuring that all SAEs are reported immediately, by e-mail (preferred) or fax, but in any case no later than 24 hours of any site staff becoming aware of the event.

Initial notification should be followed as soon as possible by detailed written reports. The initial and follow-up reports should identify subjects by unique code numbers assigned in the trial and not by the subjects' names, personal identification numbers, and/or addresses. The following information is **mandatory** for the initial report:

- Subject trial identification data (ID)
- Trial treatment (blinded, if applicable)
- Start date (time, if relevant) of the trial treatment
- Brief description of the event (diagnosis)
- Start date (time, if relevant) of the event
- Seriousness criteria

• Causality assessment

For reported deaths, the Investigator should supply the Sponsor and the IEC (if applicable) with any additional requested information (e.g. autopsy reports and terminal medical reports).

SAE REPORTING CONTACT DETAILS

[name]

FGK Drug Safety

E-mail: [contact] [contact]

In addition please notify the bioskin CTM ([name], [name]). The FGK pharmacovigilance team takes over the Sponsor's task of informing the Competent Authorities and the European Medicines Agency (EMA) of any individual case reports of SAEs that are determined to be reportable by the sponsor (i.e. adverse events considered as serious, related and unexpected [SUSARs]). SUSARs will be distributed within 7/15 working days to the EMA (EudraVigilance) and concerned Competent Authorities and the Ethics Committees, according to local regulations. The investigator will be notified by FGK of safety issues/SUSARs according to current legislation.

11.4 **Precautions/Overdose**

Since all study treatments are administered by trained trial personnel and are applied intradermally, the risk of overdose is minimal.

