5.2 Potential Risks and Benefits

No direct benefit is expected for subjects participating in early clinical trials.

Preclinical toxicity studies have not shown any clinically visible changes or histological changes after subcutaneous injections to indicate any tolerability issue.

In the First in Man (FIM) clinical trial, FOL-005 was well tolerated. No Serious Adverse Events were reported during the trial and no subject withdrew from treatment or had the treatment interrupted due to AEs. No severe AEs were reported. Local tolerability events, mostly assessed as procedure related, contributed to a majority of the reported events. These were almost exclusively of mild severity; only 2 injection site haematomas of moderate severity were reported.

There were no differences in local AE frequency between doses, ranging from 0.005 to 0.500 µg of FOL-005 or, between FOL-005 and placebo treatment. Neither were there any increases in frequency of AEs or in AE severity during treatment. In contrast, the frequency of reported local tolerance AEs decreased over time [8].

Considering the safety results in the FIM study, the foreseeable risks to the subjects of any FOL-005 related reactions are very low.

The duration of trial FCS-002, will be identical to the FIM trial and the maximum dose (single doses as well as accumulated dose) will be lower than in the FIM trial. The application areas differ however between the trials; in the FIM trial administrations were performed on the thighs and in trial FCS-002 administrations will be performed on the scalp.

The foreseeable risks of the subjects related to the trial procedures include allergic or hypersensitivity reactions to the tattoo or the disinfectants, and mild pain and local discomforts (e.g. haematoma) related to the intradermal injection of the peptide and blood samplings.

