9.4 Selection and Timing of Dose for Each Subject

The dose regime in the study, 3 times per week, is selected based on the results in the phase I/IIa trial FCS-001 where the subjects were treated 2 or 3 times per week. The efficacy measured both as increase in hair density as well as in percentage of responders, was more prominent after administration three times per week as compared to two times per week. FOL-005 was well tolerated at all tested doses and there was no detectable systemic absorption of FOL-005 at either of the dosing regimens. Injection related AEs such as haematomas and erythema, were more frequent in the group treated 3 times per week as

compared to the group treated 2 times. This is considered to be a result of the injection procedure and not the active ingredient. No increase in systemic AEs was found with the more frequent dosing.

Detailed descriptions of the treatment regimen and instructions for application of the IP are given in Section 9.1.1.

Restrictions to follow during the treatment period are described in Section 9.8.1.

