10 TRIAL ASSESSMENTS AND PROCEDURES

10.1 Endpoints

Primary endpoint:

Change from baseline of total hair density (No. of hairs per cm2) on the scalp after 12 weeks of treatment

Secondary endpoints are:

Change from baseline of total hair density (No. of hairs per cm2) on the scalp after 8 weeks of treatment

Change from baseline of hair growth parameters after 8 and 12 weeks of treatment:

- Cumulative hair thickness (mm/cm²)
- Hair thickness (µm/cm², mean median)
- Hair length (mm/cm²; mean, median)
- Terminal hair density (n/cm²)
- Vellus hair (<40µm thick) density (n/cm²)
- Total hair growth (µm/day/cm²)
- Hair growth (μ m/day/cm², mean median)
- TrichoScan Änagen/Telogen ratio
- Proportion of anagen hairs (%)
- Proportion of telogen hairs (%)
- Proportion of vellus hair (%)

To evaluate **the** safety based on:

- Any adverse events and adverse drug reactions reported
- Local tolerability assessments
- Vital signs and physical examination
- Abnormal safety laboratory parameters

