12.1.9 Adverse Events

AEs will be coded using the Medical Dictionary for Regulatory Activities (MedDRA) and tabulated by system organ class (SOC) and by preferred term.

The total number of subjects with at least 1 AE, at least one treatment emergent AE (TEAE) and the total number of AEs and TEAEs will be presented.

The number of subjects, percentage and the number of TEAEs will be tabulated by SOC and by preferred term. TEAEs will also be tabulated by severity and by relationship to treatment. In this table, subjects with TEAEs will be counted only once within a SOC or a preferred term by using the event with the worst severity or the closest causal relationship, respectively, within each category. AEs due to local tolerance issues will be presented by dose administered to the respective treatment areas.

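### The 11.2 causality scale cannot grade a needle reaction as Unlikely or unrelated to the drug, and the 11.2 AE items omit the treatment area that 12.1.9 needs

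*Combined protocol and SAP*

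**What the plan says.** The protocol's section 11.2, under Causality, offers three grades:

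- Probable: an event "with a reasonable time sequence to administration of the drug, unlikely to be attributed to concurrent disease or other drugs or" (the list of rival causes ends with chemicals). The event must also respond as one would expect when the drug is withdrawn.
- Possible: timing that fits the drug, "but which could also be explained by concurrent disease or other drugs or chemicals". Information on withdrawal may be missing.
- Unlikely: timing that makes a causal link improbable, "and in which other drugs, chemicals or underlying disease provide plausible explanations".

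The same section lists eight items for each AE: description, start, stop, severity, action taken with trial treatment, causality, seriousness and outcome. The treatment area is not among them.

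On outputs, section 10.1 includes among the safety endpoints "Any adverse events and adverse drug reactions reported". Section 12.1.9 tabulates TEAEs by relationship to treatment, counting a subject once per category at the closest relationship. It adds that "AEs due to local tolerance issues will be presented by dose administered to the respective treatment areas".

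On what to expect, section 5.2 reports from the first-in-man trial: "Local tolerability events, mostly assessed as procedure related, contributed to a majority of the reported events". Section 9.4 says of the haematomas and erythema that were more frequent with three injections a week: "This is considered to be a result of the injection procedure and not the active ingredient".

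**The concern.** The protocol regards injection reactions mainly as effects of the procedure, but its causality scale gives the investigator no way to record that view. The injection, shaving and blood sampling do not appear in any grade, and the scale has no bottom category for an event unrelated to the drug. An investigator who follows the definitions must place a needle reaction in one of the two upper grades.

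This reaches the reported results. The relationship table would show such events as at least possibly due to FOL-005, including events from a placebo area. Because each subject is counted once at the closest relationship, a needle reaction at a placebo area can set the relationship shown for that subject. The plan also does not say which grades make an event an adverse reaction, although adverse drug reactions are a named safety endpoint.

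The missing area is a second, separate gap. A by-dose table of local AEs needs to know where on the scalp the event occurred, and the AE record as specified does not ask.

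**Working it through.** No figure in the plan is in dispute, so this is mainly a comparison of texts, with a few supporting counts.

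**1. A pure needle reaction against each grade.** Take an injection-site haematoma with no relevant disease, other drug or chemical.

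| Grade | Conditions in 11.2 | Met? |
|---|---|---|
| Unlikely | Timing makes a link to the drug improbable, and a drug, chemical or disease explains the event | No on both: it follows an injection of trial treatment, and the explanation is mechanical |
| Possible | Timing fits, and disease, drug or chemical could also explain it; withdrawal data may be absent | Timing yes; alternative explanation not strictly; absent withdrawal data no obstacle |
| Probable | Timing fits, disease, drug or chemical is an unlikely cause, and there is a reasonable response on withdrawal | First two yes; third only if dosing was stopped and the event cleared |

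Unlikely is closed. Probable is open when dosing was stopped and the reaction resolved. Otherwise Possible is the nearest fit, although its wording does not strictly cover a mechanical cause either.

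**2. Which local events become AEs.** Section 10.4.6 scores erythema, haematoma, dyspigmentation, induration and pain at each visit. It reports a local sign as an AE if administration is stopped, temporarily or permanently, or is stopped at the subject's request. The local AEs entered by this route therefore come with an interruption of dosing, which is the setting in which the withdrawal condition for Probable can be met.

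**3. Can the subject number supply the dose?** Inputs: 60 subjects and 120 areas in the ratio 5:5:5:5:4 (synopsis), and no subject given the same treatment twice (section 7.1).

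- Ratio total: 5 + 5 + 5 + 5 + 4 = 24.
- Areas per active dose: 120 × 5/24 = 25.
- Placebo areas: 120 × 4/24 = 20.
- Subjects with placebo and one active dose: 20.
- Subjects with two different active doses: 60 − 20 = 40.
- Subjects whose number alone identifies the dose behind a local AE: 0 of 60.

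**4. Exposure to the procedure.** From the flow chart, treatment is given at visits 2, 3–21, 22, 24 and 25–36.

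- Visits: 1 + 19 + 1 + 1 + 12 = 34.
- Injections per completer: 34 × 2 = 68.
- Planned injections: 68 × 60 = 4,080, of which 20 × 34 = 680 are placebo.

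These are counts of injections. They show that needle reactions are foreseeable; they do not estimate how many AEs are affected.

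**The case against.** A reader might infer several stronger points, and the case against them is good.

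- *Needle and tattoo reactions all become Probable.* The documents do not support this. Probable also needs a response on withdrawal, so a haematoma that fades while dosing continues does not qualify. Tattoo ink and hair dye can be read as chemicals, which opens Possible, or Unlikely if the timing is also improbable. The initial tattoo precedes the first dose, so an early reaction to it has no time sequence to the drug.
- *Local AEs cannot be tied to a dose, or the table cannot be built.* This is not shown. Sections 12.1.9 and 12.1.11 plan presentation by dose and area, the tolerability scores must be held by area, and the event description or an eCRF field may carry the site. The eCRF is not among the documents.
- *Procedure reactions are automatically counted as reactions to FOL-005.* Section 11.1.2 defines an adverse reaction by a reasonable causal relationship, and no text converts a grade into that status.
- *The two trials cannot be compared.* The causality scale of the earlier trial is not in the documents.

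It can also be said that placebo areas receive the same injection under blinding, so comparing local events by dose separates needle from drug without any causality grade. That is correct for the by-dose tables, and it limits the damage. For AEs it works only if the area is recorded. It does not repair the relationship table, because the tolerability scores carry no causality grade and do not feed it. A planned table also does not ensure that its input is collected.

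**Conclusion.** The concern holds in two limited parts.

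First, the scale in 11.2 leaves no route by which an AE caused by the needle can be graded below Possible. The relationship table in 12.1.9 is therefore pushed towards the drug, at placebo areas as well as active ones, against the protocol's own view of such events in 5.2 and 9.4.

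Second, 12.1.9 requires local-tolerance AEs by the dose given to the area, while 11.2 does not list the area, and in all 60 subjects the subject number leaves two candidate treatments. In 20 of them one of the two is placebo.

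The number of AEs affected cannot be derived from the documents. It may be small, because under 10.4.6 the local-tolerability AEs are mainly those that led to stopping of administration. They are also the ones for which attribution to drug or needle, and to a dose, matters most.

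This rests on three assumptions: investigators apply the definitions as written; 10.4.6 is the main route by which local signs become AEs; and the eCRF adds nothing on area or procedure causality beyond the items in 11.2. If the eCRF already holds either item, that part reduces to aligning the text. The change is worth making before the eCRF is final, but it does not threaten the design.

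**What to change.** In section 11.2:

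- add a Not related grade;
- record relationship to trial procedure (injection, tattoo, dye, shaving, blood sampling) separately from relationship to IP;
- state which IP grades count as an adverse reaction in the sense of 11.1.2;
- add treatment area (1, 2, both, not local) to the AE items.

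In section 12.1.9, tabulate IP-related and procedure-related TEAEs separately, and base the by-dose presentation of local AEs on the recorded area.

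The cost is two eCRF fields, one added response option, slightly longer AE entry and one extra table. Dosing, visits and sample size are unaffected.
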